#### **2.8.1.1 Adverse events of special interest / grouping of AEs**

##### **Data analysis of AESIs**

Adverse events of special interest (AESIs) are defined as AEs within the following categories/groupings of PTs:

- Cutaneous squamous cell carcinoma (including keratoacanthomas)
- Treatment emergent malignancies (excluding cuSCC, basal cell carcinoma)
- Pyrexia
- Uveitis
- Renal failure/acute renal failure
- Pancreatitis

- Hypersensitivity
- Hyperglycaemia

AESIs are defined at the project level and may be updated based on emergent data to reflect new AESIs of interest at the time of analysis.

For each specified AESI, number and percentage of subjects with at least one event of the AESI occurring during on treatment period will be summarized.

A listing of all grouping levels down to the MedDRA preferred terms used to define each AESI will be generated.

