### 1.3. Trametinib

Trametinib (GSK1120212), a pyrido-pyrimidine derivative, is a potent and highly selective allosteric i.e. non-ATP competitive inhibitor of MEK1 and MEK2 activation and kinase activity. In the pivotal study MEK114267 (METRIC), 322 patients who had metastatic melanoma with a V600E or V600K BRAF mutation were randomized in a 2:1 ratio to receive trametinib (2 mg orally) once daily or chemotherapy (either intravenous dacarbazine, 1000 mg per square meter of body-surface area or paclitaxel 175 mg per square meter every 3 weeks.) Median progression-free survival was 4.8 months in the trametinib group and 1.5 months in the chemotherapy group (hazard ratio 0.45; 95% confidence interval [CI], 0.33 to 0.63;  $P < 0.001$ ). At 6 months, the rate of overall survival was 81% in the trametinib group and 67% in the chemotherapy group despite crossover (hazard ratio, 0.54; 95% CI, 0.32 to 0.92;  $P = 0.01$ ). Rash, diarrhea, and peripheral edema were the most common toxic effects in the trametinib group and were managed with dose interruption and dose reduction; asymptomatic and reversible reduction in the cardiac ejection fraction and ocular toxic effects occurred infrequently. Secondary skin neoplasms were not observed [Flaherty, 2012a]. Data from this trial were the basis for the approval of trametinib for patients with unresectable or metastatic melanoma with BRAF V600E or V600K mutations as detected by an FDA-approved test.

Trametinib monotherapy has been evaluated in well over 500 patients. Common AEs include rash, lymphedema, and diarrhea. In addition, a decrease in left-ventricular ejection fraction (LVEF) has been observed in approximately 10% of subjects receiving trametinib. Most of these cases were associated with no symptoms. Consequently, strict monitoring has been in place along with guidelines on management of patients with decreased LVEF.

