### **5.7. Dose Modification Guidelines**

The severity of AEs will be graded using the CTCAE, version 4.0. The section includes:

- general guidelines for clinically significant toxicities related to study treatments and
- specific guidelines for adverse events of special interest, which are events that have been observed with higher frequency or severity in subjects receiving dabrafenib, trametinib, or a combination of both therapies.

With the exceptions of pyrexia which is likely related to dabrafenib, and LVEF decrease, retinal vein occlusion (RVO), central serous retinopathy (CSR), and retinal pigment epithelial detachment (RPED) which are likely related to trametinib, guidance suggests that both therapies be reduced simultaneously in response to toxicities that are considered by the investigator to be treatment related.

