### **5.7.3.2. Hypertension**

Increases in blood pressure have been observed in subjects receiving trametinib. Recommendations for blood pressure monitoring and management are provided in Section 5.7.3.2.1 and Section 5.7.3.2.2, respectively.

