### 5.7.5.5. Guidelines for Pneumonitis

Pneumonitis has been observed in subjects receiving trametinib. To reduce the risk of pneumonitis, subjects will be monitored closely for symptoms, evaluated with imaging and functional tests. Dose modification and supportive care guidelines for pneumonitis are described in [Table 16](#).

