# **4 Change to protocol specified analyses**

- The primary endpoints and secondary endpoints will not be analyzed as in protocol.
- Clinical laboratory data, vital signs, 12-lead ECG, and ECHO/MUGA scan data will not be summarized and listed.

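### The SAP's list of adverse events of special interest does not match the protocol's and omits all four events the protocol calls likely related to trametinib, so the AESI table and listing cannot show them

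*SAP*

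**What the plan says.** Protocol 5.7 says that it contains "specific guidelines for adverse events of special interest, which are events that have been observed with higher frequency or severity", and ties this to subjects given dabrafenib, trametinib or both. Table 3 lists the events that have such guidelines, and its footnote sends the reader to 5.7.4.3 for cuSCC. The heading of 5.7.5 introduces pyrexia, diarrhoea, renal insufficiency, visual changes and pneumonitis as the other events of special interest, which implies that the cardiovascular and skin groups before it also belong to the set.

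On attribution, Protocol 5.7 names "LVEF decrease, retinal vein occlusion (RVO), central serous retinopathy (CSR), and retinal pigment epithelial detachment (RPED) which are likely related to trametinib". Section 5.7.3.2 adds "Increases in blood pressure have been observed in subjects receiving trametinib", and 5.7.5.5 adds "Pneumonitis has been observed in subjects receiving trametinib". Section 1.3 reports that "a decrease in left-ventricular ejection fraction (LVEF) has been observed in approximately 10% of subjects receiving trametinib".

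Protocol 9.2.4.3.2 undertakes to summarise the characteristics of these events separately. Protocol 9.2.4 asks that departures from, or additions to, the analysis plan be documented in the Reporting and Analysis Plan and the final report.

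SAP 2.8.1.1 introduces its own list: "Adverse events of special interest (AESIs) are defined as AEs within the following categories/groupings of PTs". The groups are cuSCC, other treatment-emergent malignancies, pyrexia, uveitis, renal failure, pancreatitis, hypersensitivity and hyperglycaemia. The SAP adds that the list is set at project level and may be updated as data emerge. SAP section 4 declares two changes from the protocol. One is that the primary and secondary endpoints will not be analysed as planned. The other is that "Clinical laboratory data, vital signs, 12-lead ECG, and ECHO/MUGA scan data will not be summarized and listed". The AESI set is not mentioned.

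**The concern.** The AESI table is where a reader looks first for toxicities known in advance to matter with these drugs. If a group is not defined, its absence from the table does not mean that no event occurred, and the table gives no sign of this. Here the undefined groups include every event that the protocol singles out as likely related to trametinib. Trametinib is part of Cohort B's pre-operative treatment, and under Protocol section 3 subjects of either cohort with remaining disease may resume on the combination after surgery. So the gap can affect subjects in both columns of the table.

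The dropped safety outputs add to this. With no echocardiogram or vital-sign display, a fall in LVEF or a rise in blood pressure is visible only if the investigator recorded it as an adverse event.

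**Working it through.** The plan states no figure that could be reproduced, so the check sets the two lists side by side.

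**Protocol set.** Table 3 has 11 specific rows: LVEF, hypertension, QTc, rash, hand-foot skin reaction (HFSR), pyrexia, diarrhoea, renal insufficiency, visual changes, pneumonitis and liver chemistry. The footnote adds cuSCC: 11 + 1 = 12.

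**SAP set.** 8 groups, identical in 2.8.1.1 and in the note to Table 14.3.1-1.9.

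| Protocol 5.7 group | In SAP list? |
|---|---|
| cuSCC | Yes |
| Pyrexia | Yes |
| Renal insufficiency | Yes, as renal failure |
| Visual changes | In part: uveitis only; RVO, CSR and RPED absent |
| LVEF decrease | No |
| Hypertension | No |
| QTc prolongation | No |
| Rash | No |
| HFSR | No |
| Diarrhoea | No |
| Pneumonitis | No |
| Liver chemistry | No |

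Count: 3 full + 1 partial + 8 absent = 12. In the other direction, 8 − 4 = 4 SAP groups have no row in the protocol set: other malignancies, pancreatitis, hypersensitivity and hyperglycaemia.

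**Events tied to trametinib.** The protocol calls four likely related to it (LVEF decrease, RVO, CSR, RPED); 0 of 4 are in the SAP list. It describes two more as seen in subjects receiving it (hypertension, pneumonitis); 0 of 2 are in the list. The one eye event kept, uveitis, is the one that Protocol 5.7.5.4 associates with dabrafenib.

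**Where the missing events can still appear.**
- SAP 2.8.1 summarises all on-treatment AEs by system organ class, preferred term and maximum grade, and lists every AE. Table 14.3.1-1.1 shows them by cohort.
- Protocol 7.3.1.2 makes CSR, RVO and Hy's Law liver events protocol-specific SAEs. Protocol Table 15 requires diagnosed RVO and RPED to be reported as SAEs. These reach the SAE outputs.
- Protocol 7.3.1.3 has an AE recorded for any safety assessment that leads to an intervention, so an LVEF fall that triggers the action in Protocol Table 6 becomes an AE.
- None of these routes leads into Table 14.3.1-1.9 or Listing 16.2.7-1.2.

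**Scale.** For illustration, assume the roughly 10% LVEF rate in Protocol 1.3 applied to each trametinib-exposed subject here. The chance of at least one event among n exposed subjects is 1 − 0.9^n: 10% for n = 1 and 1 − 0.531 = 47% for n = 6. The SAP does not say how many of the 6 received trametinib, and the 10% comes from monotherapy with exposure of unstated length. The range shows only that an event is possible and that most rows would probably be empty.

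**The case against.** The strongest case against has four parts.

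First, the SAP says its list is a project-level convention open to update. That is true, but the clause obliges nobody to add a group and does not acknowledge the protocol's set.

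Second, Table 3 is titled as a list of dose-modification categories, and Protocol 9.2.4.3.2 points to section 7.3.1, which contains no AESI list. So the protocol never enumerates the set in one labelled place. This stands as a caution about the 8-of-12 count. It does not remove the mismatch: the text of 5.7 and the heading of 5.7.5 both use the term for these events, and section 7.3.1 itself singles out CSR, RVO and Hy's Law events, which the SAP list also lacks.

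Third, a reader might infer that the outputs are blind to the added toxicity of the combination, or would make it look as if it carried only dabrafenib-type risk. The documents do not support that. Every AE remains listed and tabulated by cohort, and the serious retinal and liver events reach the SAE outputs. Pyrexia, renal events and cuSCC, which the protocol also reports with the combination, are retained. Nor does the SAP omit everything linked to trametinib: renal insufficiency is marked for both drugs in Table 3 and is kept. Hypertension and pneumonitis are also marked for both drugs, so their attribution is weaker than that of the four named events.

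Fourth, Protocol section 2 plans no statistical comparison between cohorts, and the table is split by cohort rather than by treatment received. Adding groups would therefore not separate the two regimens. In addition, the dropped laboratory, vital-sign, ECG and echocardiogram outputs are openly declared, and Table 19 schedules ECG at screening only, so losing ECG output costs little for QTc. All of this stands, and it limits the point to the AESI outputs.

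**Conclusion.** The mismatch is real and undeclared. Against the set in Protocol 5.7, the SAP list covers 3 of 12 groups fully and 1 in part, and none of the four events the protocol calls likely related to trametinib. As written, Table 14.3.1-1.9 and Listing 16.2.7-1.2 cannot show those four, nor hypertension, pneumonitis, rash, HFSR, diarrhoea, QTc prolongation or liver events.

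The consequence is modest. It concerns descriptive completeness in a study terminated with 6 subjects, and it affects one table and one listing. It does not hide the events from the study report or bias any inference, because none is planned. It carries some extra weight for LVEF and blood pressure, which have no measured-data display left.

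Two assumptions underlie the count: that Table 3 with its footnote is the protocol's AESI set, and that the SAP's named groups do not absorb the missing terms through their preferred-term lists. The SAP does not give those lists; a broad hypersensitivity group, for instance, might take in some rash terms.

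**What to change.** Keep the eight existing groups. In SAP 2.8.1.1 and in the programming note to Table 14.3.1-1.9, add preferred-term groupings for LVEF decrease, RVO/CSR/RPED, hypertension, pneumonitis, rash, HFSR, diarrhoea, QTc prolongation and hepatic events, and carry the same set into Listing 16.2.7-1.2. A note in SAP section 4 could record that four groups go beyond the protocol's set. Such a note alone would not be enough, because the outputs would still be unable to show the missing events.

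The cost is wording in two places, the groupings, and their programming for six subjects. No new data are collected. The drawback is a longer, mostly empty table, but an empty row would then mean that no such event was reported.

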### **2.8.2 Deaths**

Separate summaries for on-treatment death and all deaths on-treatment and post-treatment will be produced by system organ class and preferred term. All deaths will be listed, post treatment deaths will be flagged.

Note: The death summaries cover subjects from the Safety Set.

### **2.8.3 Laboratory data**

As a short close-out CSR will be produced, data will not be summarized and listed.

### **2.8.4 Other safety data**

#### **2.8.4.1 ECG and cardiac imaging data**

As a short close-out CSR will be produced, data will not be summarized and listed.

#### **2.8.4.2 Vital signs**

As a short close-out CSR will be produced, data will not be summarized and listed.

## **2.9 Pharmacokinetic endpoints**

Please refer to Section 2.5 and Section 2.7 for primary and secondary PK-related endpoints.

## **2.10 PD and PK/PD analyses**

Not applicable.

## **2.11 Patient-reported outcomes**

Not applicable.

## **2.12 Biomarkers**

As a short close-out CSR will be produced, biomarker data will not be summarized. The biomarker data will be listed, if data permit.

## **2.13 Other Exploratory analyses**

Not applicable.

## **2.14 Interim analysis**

No formal interim analysis is planned for this study.

# **3 Sample size calculation**

## **3.1 Primary analysis**

For the objective of estimating the levels of dabrafenib its metabolites, and trametinib in brain metastases, the average level for the parent drug and each metabolite along with the range and 95% confidence interval for the brain metastases, extracranial metastases, and plasma will be reported. A sample size of 15 patients per cohort was chosen to characterize concentrations with reasonable precision (within 0.7 standard deviation) within each cohort. The correlation and corresponding 95% confidence interval between concentrations in the brain metastases and concentrations in the plasma, and in the optional extracranial metastases and CSF, for the parent drug and each metabolite will also be estimated. Additionally, the ratio between the concentrations in the brain metastases and in the extracranial metastases and the plasma concentrations within each subject for each metabolite will be estimated and summarized with 95% CI's.

Due to the difficulty in recruiting patients, this study was terminated early, 6 patients were enrolled to study at termination of study.

## **3.2 Power for analysis of key secondary variables**

Not applicable.

# **4 Change to protocol specified analyses**

- The primary endpoints and secondary endpoints will not be analyzed as in protocol.
- Clinical laboratory data, vital signs, 12-lead ECG, and ECHO/MUGA scan data will not be summarized and listed.

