**Endpoint**

hydroxy-, carboxy- and desmethyl-dabrafenib) and trametinib (Cohort B only) in CSF samples.

Changes in MAPK pathway markers in paired extracranial biopsies taken pre-treatment, during craniotomy, and at disease progression, and changes in markers between post-operative intracranial and extracranial biopsies, when data is available.

Changes in the radiographic characteristics of the tumors will be compared to (1) levels of dabrafenib, its metabolites and trametinib (where appropriate) in the brain metastases, plasma, and CSF, and (2) MAPK pathway activation status in tumors at the time of surgery. When available, results will also be compared to the analysis of early clinical responses in extracranial metastases, as determined by the PET-CT imaging.

- change from baseline to pre-surgery in the sum of the longest diameters of intracranial target lesions,
- maximum change from baseline to pre-surgery in the sum of longest diameters of unresected intracranial target lesions,
- overall extracranial response rate in unresected lesions, and
- overall survival

Safety as measured by clinical assessments including vital signs and physical examinations, 12-lead electrocardiograms (ECG), echocardiogram (ECHO), chemistry and hematology laboratory values, and adverse events (AEs).

Quantitative analysis of DNA from the brain and extracranial metastases to determine the degree of concordance of BRAF mutations between the two samples. Additional mutations found in the analysis of tumor samples will be summarized.

The expression and activation of protein signaling pathways and transcriptional networks, including the MAPK pathway, will be evaluated when available in extracranial biopsies taken pre-treatment, at/near the time of craniotomy, and at disease progression to understand changes induced by the given treatments and their correlation with other molecular features (i.e. mutations) and treatment outcomes.

The expression and activation of protein signaling pathways and transcriptional networks, including the

---

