**Endpoint**

MAPK pathway, in intracranial and, when available, extracranial biopsies collected at/near the time of craniotomy, and/or at disease progression, will be compared to identify differential molecular features and treatment effects.  
Results will also be compared to the analysis of early clinical responses in extracranial metastases, as determined by the PET-CT imaging, and drug levels in blood and tissue samples.

Since study is terminated with 6 enrolled patients, a short close-out CSR will be produced. The planned objectives and endpoints will not be fully analyzed.

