### **On-treatment assessment/event and observation periods**

The overall observation period will be divided into three mutually exclusive segments:

**Pre-treatment period** is defined as from day of patient's informed consent to the day before first administration of study treatment

**On-treatment period** is defined as from date of first administration of study treatment to 30 days after date of last actual administration of study treatment (including start and stop date)

**Post-treatment period** is defined as starting at day 30+1 after last administration of study treatment.

Notes: if data on clock time is available in the clinical database (e.g. for time of blood/urine sample taken, ECG performed, etc. and first study treatment administration), a more precise distinction between pre-treatment and on-treatment periods is encouraged to be used. If dates are incomplete in a way that clear assignment to pre-, on-, post-treatment period cannot be made, then the respective data will be assigned to the on-treatment period.

Safety summaries (tables, figures) include data from the pre-treatment period (to display the baseline status e.g. for ECG) and the on-treatment period, i.e. data from the post-treatment period with the exception of deaths should not be included unless requested from Health Authorities or external committees.

In particular, summary tables for adverse events (AEs) will summarize only on-treatment events, with a start date during the on-treatment period, the so-called *treatment-emergent* AEs.

However, all safety data (including those from the post-treatment period) will be listed and those collected during the pre-treatment and post-treatment period are to be flagged.

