## **2.5 Analysis of the primary objective**

### **2.5.1 Primary endpoint**

As a short close-out CSR will be produced, summary analyses will not be performed. The concentration and distribution (when applicable) of dabrafenib, dabrafenib metabolites and trametinib (Cohort B only) will be listed for each cohort by tissue type (i.e., parenchymal brain metastases, optional assessment of extracranial metastases, plasma) and by pre-craniotomy phase and post-craniotomy phase. Both absolute concentrations and ratios relative to plasma will be determined for the different sample types, if data permit.

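### Laboratory, vital-sign and ECG/ECHO values are dropped from listings as well as summaries, although SAP 2.1.1 says all safety data are listed; listing them for the at most 6 treated subjects would be a cheap improvement

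*SAP*

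**What the plan says.** SAP 2.1.1, in its paragraphs on observation periods, says without exception that "all safety data (including those from the post-treatment period) will be listed", with pre- and post-treatment records flagged. It also says that safety summaries bring in pre-treatment data "to display the baseline status e.g. for ECG".

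SAP 2.8.3 then says of laboratory data: "As a short close-out CSR will be produced, data will not be summarized and listed". Sections 2.8.4.1 (ECG and cardiac imaging) and 2.8.4.2 (vital signs) repeat that sentence. Section 4 records the omission as a change from the protocol: "Clinical laboratory data, vital signs, 12-lead ECG, and ECHO/MUGA scan data will not be summarized and listed".

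The endpoint table in SAP 1.2 still defines the safety endpoint as "Safety as measured by clinical assessments including vital signs and physical examinations, 12-lead electrocardiograms (ECG), echocardiogram (ECHO), chemistry and hematology laboratory values", together with adverse events. The section closes with the caveat that "The planned objectives and endpoints will not be fully analyzed". SAP 3.1 gives the reason: recruitment was difficult and "6 patients were enrolled to study at termination of study".

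Protocol 9.2.4.3.3 planned summaries of haematology and chemistry by CTCAE grade. Protocol 9.2.4.3.4 planned both summaries and full listings of the other scheduled safety measures, including vital signs, ECG and echocardiogram.

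For PK the SAP makes a different choice under the same close-out constraint. Section 2.5.1 drops summaries, but the concentrations "will be listed for each cohort by tissue type", and Section 2.7 treats CSF concentrations the same way.

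**The concern.** Stopping at 6 enrolled subjects is a good reason to drop summary tables. It is a weaker reason to drop listings, because by-subject listings are the natural substitute for summaries in a very small study, and the SAP uses them that way for drug concentrations.

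The omitted measures are named components of the safety endpoint. For any result that did not become an adverse event, a reader of the close-out report could not tell whether the measure was normal, had changed, or was never taken.

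LVEF is the clearest example. Protocol 1.3 reports a decrease in about 10% of trametinib subjects, mostly without symptoms, and subjects in either cohort may receive trametinib after surgery.

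**Working it through.** No design figure is involved, so the check is a comparison of the texts, followed by an illustrative count.

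**1. What the wording means.** Taken alone, the phrase in Sections 2.8 and 4 could mean 'not both summarized and listed'. The shells settle it. The output table of contents covers disposition, analysis sets, demographics, exposure and dosing, deaths, adverse events, AESIs and PK concentrations. The Section 16.2 listings end at 16.2.7. Outputs showing laboratory, vital-sign, ECG or ECHO values: 0 tables and 0 listings. The phrase means neither.

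**2. What the adverse event outputs still capture.** Protocol 7.3.1.3 requires an adverse event for any result that led to an intervention, including interruption, dose reduction or discontinuation. That covers the liver stopping criteria (5.7.6.1) and an LVEF fall of more than 10% to below LLN (Table 6, which requires interruption). Protocol 7.3.1.2 makes Hy's Law events SAEs.

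**3. What they can miss.** This depends on how 7.3.1.3 is read.
- If every abnormal result is an adverse event, few changes are lost.
- If only clinically significant results are, several changes can go unrecorded:
  - an LVEF fall of more than 10% that stays at or above LLN, for which Table 6 gives no action (LVEF decrease is also not on the AESI list in SAP 2.8.1.1);
  - a creatinine rise above 0.2 and up to 0.5 mg/dL, with treatment continued (Table 14);
  - ALT from 3 to below 5 times ULN, with treatment continued (5.7.6.2), where the liver event form need not be completed unless the elevation persists for 4 weeks or weekly monitoring is not possible (7.3.1.6).
- On either reading, 7.3.1.3 keeps clinically significant results associated with the underlying disease out of adverse event reporting unless they are worse than expected.
- On either reading, the measured values and any record that a test was not done are absent.

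**4. Illustrative count of values not shown.** Six were enrolled, so at most 6 were treated. Tests come from Protocol Table 21, vital signs from 7.3.7 and 7.11, and visits from Table 19. Three visits means screening, the day before surgery and one later visit.
- Haematology and chemistry: 10 + 13 = 23 tests. Screening only: 23 × 6 = 138. Three visits: 23 × 3 = 69 per subject, and 69 × 6 = 414.
- Coagulation (PT, PTT, INR): 3 × 6 = 18 at screening, or 3 × 2 × 6 = 36 with the day before surgery.
- Vital signs: 5 × 6 = 30 at screening. Over three visits, with 4 values at a discontinuation visit, 5 + 5 + 4 = 14 per subject, and 14 × 6 = 84.
- LVEF: 6 baseline values plus 0 to 6 at Week 8, the first scheduled repeat, so 6 to 12.

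These are not upper bounds. Subjects who resume treatment have chemistry and haematology every 4 weeks. The top exposure category in the SAP shells is 60 weeks or more. If one subject reached 60 weeks after restart, 60 / 4 = 15 visits, and 15 × 23 = 345 results for that subject alone.

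**The case against.** The strongest reply is that the omission is deliberate, declared and consistent. Protocol 9.2.4 requires departures from the planned analysis to be documented in the analysis plan and final report, and SAP 4 does this. SAP 1.2 warns that endpoints will not be fully analysed. Survival analysis, protocol deviations and individual efficacy data are dropped too. The specific sections and the shells agree with each other, so they override a general sentence in 2.1.1, and a programmer would not be misled. All of this stands. If the wording conflict were the whole point, it would be editorial.

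Two further replies also have force. PK concentrations are the primary endpoint, so it is natural to keep them ahead of routine monitoring data. And for laboratory data, the protocol's own section (9.2.4.3.3) promises summaries only, so for that domain the listing commitment rests mainly on SAP 2.1.1.

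Neither reply shows why listing without summarizing, the SAP's own close-out solution, should not extend to a few by-subject safety listings.

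A reader might infer more: that safety findings are being withheld, or that serious toxicity would go unreported. The documents do not support that. The change is stated openly, interventions and Hy's Law events reach the adverse event outputs, and nothing shows how many other changes there were, if any.

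**Conclusion.** The point holds as a minor one. SAP 2.8.3, 2.8.4.1, 2.8.4.2 and 4 remove from every planned output the values of measures that SAP 1.2 keeps in the safety endpoint. That goes against SAP 2.1.1 and, for vital signs, ECG and ECHO, against Protocol 9.2.4.3.4.

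The loss is confined to measured values, completeness of testing, and changes that did not become adverse events. How many changes fall in the last group depends on the reading of Protocol 7.3.1.3 and cannot be estimated. The counts above describe volume of data under assumed visit numbers. A reader might take 414 as a ceiling or as a number of missed safety findings, and it is neither.

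The decision to produce no summary tables is sound and is not challenged.

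**What to change.** In SAP 2.8.3, 2.8.4.1, 2.8.4.2 and 4, change the instruction to 'listed, not summarized'. Add by-subject, by-visit Section 16 listings for the treated subjects (at most 6):
- haematology, chemistry and coagulation: raw values with reference-range flags, and CTCAE grade only if already available, since SAP 5.3 contains no laboratory derivations;
- vital signs;
- LVEF: value, change from baseline, below-LLN flag, and 'not done' where missing.

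For ECG, which Table 19 schedules only at screening, either list that result or name it as an exception. Align both sentences in 2.1.1 (the listing of all safety data and the ECG baseline example) with Section 2.8.

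The cost is three or four extra programmed listings from data the protocol already collects, and a somewhat longer close-out report. The laboratory listing will be longer for any subject with prolonged treatment after surgery.
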